8.3.5 EVENT REPORTING

Adverse events and serious adverse events that will be tracked for this study are described in 8.4.1. Considering the nature of the study, we expect most of these events will be considered unrelated to the study procedures, including serious adverse events, like suicide attempts. If AEs/SAEs occur, the following procedure will be activated:

The research staff member who observes or is notified of an adverse event (e.g., significant distress during the baseline assessment) will notify the Principal Investigator (or his/her designee) on the same business day. The PI (or his/her designee) will complete an Adverse Event Form for each event and will determine if the event is an SAE. If the AE is determined to be an SAE, the Serious Adverse Event Form will be completed.

All reports will be made in writing to the NIMH DSMB representative, NIMH Program Official (PO), and sIRB. These reports should indicate that the monitoring entities (i.e., the PI and IRB, and/or DSMB) and appropriate regulatory entities (e.g., OHRP, FDA) have been notified in accordance with the approved monitoring plan and federal regulations. Reports will be submitted to the monitoring entity (e.g., NIH-DSMB) at least annually or on a schedule determined by the monitoring entity's policy. Monitoring entities may require more frequent reporting.

To local IRB and Sponsor

Any AE is reportable to the sIRB and local IRB within 5 business days *when it meets the following definition:*

Any harm experienced by a subject or other individual that, in the opinion of the investigator, is *unexpected AND at least probably related* to the research. (Note: A harm is *at least probably related* to the research if in the opinion of the investigator the research procedures more likely than not caused the harm.)

All AE/SAEs with an onset date after the subject signs consent for study participation will also be reported to the IRB at the time of annual renewal. Details of the event will include severity, relationship to study intervention, duration, action taken, and outcome. All AE/SAEs that are considered related to the study intervention will be followed to resolution, or stabilization if improvement is not expected. AE/SAEs that completely resolve and then recur will be recorded as a new AE/SAE. AE/SAEs that are considered related to the study intervention and continue at 30 days post-last intervention will have a comment in the source documents by the site PI that the event has stabilized or is not expected to improve.

To NIMH DSMB

All AEs and SAEs will be reported to the NIMH DSMB in data reports prepared three times annually. Details of the event will include the AE, severity, expectedness, relationship to study intervention, duration (start/stop date), action taken, and outcome.

In addition, SAEs will be reported to the NIH DSMB within 72 business hours of the site PI's awareness of the event.

All AE/SAEs that are considered **related** to study intervention must be followed to resolution or stabilization if improvement is not expected. AE/SAEs that completely resolve and then recur should be recorded as a new AE/SAE. AE/SAEs that are considered related to study intervention and continuing at 30 days post-last intervention should have a comment in the source documents by the PI that the event has stabilized or is not expected to improve. Other supporting documentation of the event may be requested by the DSMB/NIMH and should be provided as soon as possible.

DSMB/Regulatory reporting criteria for the PI are presented in Table 6.

Table 6. DSMB/Regulatory Reporting Criteria for Study PIs		
	Related to Intervention	NOT Related to Intervention
Expected Event	DSMB Tri-Annually	DSMB Tri-Annually
Unexpected Event	DSMB Immediately	DSMB Tri-Annually
Death	DSMB Immediately	DSMB Immediately

*Note: DSMB Immediately = The AE/SAE should be reported as soon as possible to the NIMH DSMB, within **3 business days**. The SAE will also be included in the SAE section of the next DSMB Report.*

Table 7 defines the reporting requirements for a variety of study related events.

Table 7. Study Reporting Requirements.		
Reportable Event	When is Event Reported to the NIMH	Reported By
IRB or DSMB Suspensions or Terminations	Any suspension or termination of approval must include a statement of the reason(s) for the action and must be reported promptly to the NIMH PO within 3 business days of receipt .	Regulatory or Monitoring Entity and Investigator
Deaths related to study participation	Deaths must be reported immediately (no later than within 3 business days) of the principal investigator first learning of the death.	Investigator
Expected and Unexpected Serious Adverse Events related to study participation	Reported to the NIMH PO within 3 business days of the study team becoming aware of the SAE.	Investigator
Unanticipated Problems Involving Risks to Participants or Others	Reported to the NIMH PO and NIMH-DSMB representative within 3 business days of the investigator learning of the event.	Investigator
Serious or Continuing Noncompliance	Reported to the NIMH PO and NIMH-DSMB representative within 3 business days of IRB determination.	Institution
Adverse Event	For all AEs that are deemed expected and/or unrelated to the study, a summary should be submitted to the NIMH PO with the annual progress report .	Investigator
Protocol Violations	With the annual progress report .	Investigator

8.4 UNANTICIPATED PROBLEMS

8.4.1 DEFINITION OF UNANTICIPATED PROBLEMS

This protocol uses the definition of Unanticipated Problems as defined by the Office for Human Research Protections (OHRP). OHRP considers unanticipated problems involving risks to

participants or others to include, in general, any incident, experience, or outcome that meets **all** of the following criteria:

- Unexpected in terms of nature, severity, or frequency given (a) the research procedures that are described in the protocol-related documents, such as the Institutional Review Board (IRB)-approved research protocol and informed consent document; and (b) the characteristics of the participant population being studied;
- Related or possibly related to participation in the research (“possibly related” means there is a reasonable possibility that the incident, experience, or outcome may have been caused by the procedures involved in the research); and
- Suggests that the research places participants or others at a greater risk of harm (including physical, psychological, economic, or social harm) than was previously known or recognized.

8.4.2 UNANTICIPATED PROBLEMS REPORTING

The investigator will report unanticipated problems (UPs) to the reviewing Institutional Review Board (IRB), the NIMH DSMB, and to the Duke Data Center (DDC)/lead principal investigator (PI). The UP report will include the following information:

- Protocol identifying information: protocol title and number, PI's name, and the IRB project number
- A detailed description of the event, incident, experience, or outcome
- An explanation of the basis for determining that the event, incident, experience, or outcome represents an UP
- A description of any changes to the protocol or other corrective actions that have been taken or are proposed in response to the UP

To satisfy the requirement for prompt reporting, UPs will be reported using the following timeline:

- UPs that are serious adverse events (SAEs) will be reported to the IRB, the NIMH DSMB, and to the DDC/study sponsor/funding agency within **3 business days** of the investigator becoming aware of the event
- Any other UP will be reported to the IRB, the NIMH DSMB, and to the DDC/study sponsor/funding agency within 5 business days of the investigator becoming aware of the problem
- All UPs should be reported to appropriate institutional officials (as required by an institution's written reporting procedures), the supporting agency head (or designee), and the Office for Human Research Protections (OHRP) within 10 working days of the IRB's receipt of the report of the problem from the investigator

9 STATISTICAL CONSIDERATIONS

9.1 CAMPUS TRIAL STATISTICAL HYPOTHESES

The statistical hypotheses and endpoints have been previously summarized in Section 3 above.

9.2 CAMPUS TRIAL SAMPLE SIZE DETERMINATION

Power for Aim 1:

Sample size for the study is based primarily on Aim 1, although we also provide effect size (ES) estimates for the other aims given the proposed sample size. With respect to Aim 1, with a total sample of 480, the approach provided by Crivello and colleagues^{178,179,180} guarantees that the adaptive intervention with the lowest estimated mean suicide risk (ideation + behaviors) at post-treatment is, in fact, the best adaptive intervention with 90% probability. This calculation assumes that the best two ATSSs differ by $d = 0.25$ (or ≥ 2 points on the SSI), which corresponds to a small ES estimate.¹⁸¹

Power for Aim 2:

Aim 2 is a two-sample comparison (cells A+B+C vs. D+E+F). Using a two-side, two-sample t-test based on Type-I error rate of 2.5%, a sample of 240 randomized to each Stage 1 treatment arm (N=480 total), we will have 85% power to detect a small, standardized ES of $d = 0.30$ in the between groups difference in change on the primary outcomes. Based on prior studies and our pilot data with $SD=7$ for SSI,¹¹³ this ES corresponds to a clinically meaningful difference of 2 in the SSI. Note that this is a conservative estimate of power: in the repeated measures LMM, power increases in proportion to the within person correlation in baseline to 26-week SSI which can be as high as 0.40 ($p < .01$, based on pilot data). At 3-month follow-up (assuming a baseline to 48-week within correlation of 0.3) we will have 94% power to detect the same moderate ES.

Power for Aim 3:

Assuming about 50% response (N=240) and about 50% insufficient response rate [N=240, which is chosen to be slightly higher for a value divisible by the four possible treatment paths from Stage 1 to Stage 2 (CAMS-CAMS, CAMS-DBT, TAU-CAMS, and TAU-DBT) (based on pilot data)] to Stage 1 treatments corresponding to N=60 potential student participants to be randomized to each of the 4 Stage 2 arms among the non-responders as illustrated in the Schema Figure in section 1.2. We anticipate an at most Stage 1 attrition rate of about 25% among those with an insufficient response leaving N=180 total student participants to be randomized in Stage 2 (approximately 45 student participants per ATS). Estimates of attrition are chosen as equal across each treatment path but are in essence worst case scenarios, where we may see less attrition for specific treatment paths compared to others; therefore, all power estimates are conservative, with more power achievable with more available student participants for different treatment combinations. Based on the method outlined by Oetting and colleagues¹⁸² and a within-person correlation of 0.60, 2.5% Type-I error, we will have over 80% power to detect a difference of ≥ 3.4 ($d = 0.34$) in change in SSI between DBT vs. CAMS.

Power for Aims 4 and 5:

Best practices for power calculations for mediation and moderation models within SMART designs are still debated. For mediation, we will use the work of Fritz and MacKinnon,¹⁸³ who document sample size requirements to guarantee 80% power under the sequential regression framework¹⁶⁶ and the formulas of Vittinghoff et al.¹⁸⁴ Under the assumption of a medium effect for intervention on the mediator and a medium effect for intervention on outcome covarying

the mediator, and an alpha=0.025, the total sample size is calculated as N=166. Therefore, our design consisting of a sample size of 480 within Stage 1 and at least 90 subjects per two Stage 2 arms (CAMS vs CC-DBT) (N=180 total), is sufficiently powered to detect mediation within Stage 2. For moderation, we use Cohen's¹⁸¹ power tables, our sample size of 480 at the start of Stage 1 and at least 90 subjects per arm at Stage 2 is more than sufficient to detect a medium-to-large ES for a moderator.

Table 8. The 4 Adaptive treatment strategies embedded in the proposed SMART					
Adaptive Treatment Strategy	Stage 1 Treatment	Status at End of Stage 1	Stage 2 Treatment	Cells Involved in Comparisons	
1	CAMS	Responder	Maintenance/ Monitoring	A	A + B
		Insufficient Responder	Continue CAMS	B	
2	CAMS	Responder	Maintenance/ Monitoring	A	A + C
		Insufficient Responder	Switch to CC-DBT	C	
3	TAU	Responder	Maintenance/ Monitoring	D	D + E
		Insufficient Responder	Switch to CAMS	E	
4	TAU	Responder	Maintenance/ Monitoring	D	D + F
		Insufficient Responder	Switch to CC-DBT	F	

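### Section 9.2 defines its 2.5% error rate as two-sided only for Aim 2; at that level, standard analyses on the current visits do not reach the powers stated for Aim 3 and for Aim 2 at follow-up

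*Combined protocol and SAP*

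**What the plan says.** All the power statements are in Section 9.2.

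- **Aim 2.** The test is specified: "Using a two-side, two-sample t-test based on Type-I error rate of 2.5" per cent, with "a sample of 240 randomized to each Stage 1 treatment arm (N=480 total"). The result is "we will have 85% power to detect a small, standardized ES of $d = 0.30". The SD is given: "Based on prior studies and our pilot data with $SD=7$ for SSI".
- **Aim 2 at 3-month follow-up.** With a baseline-to-follow-up correlation of 0.3, "we will have 94% power to detect the same moderate ES". Neither alpha nor sidedness is restated. The only account of how the correlation enters is that "in the repeated measures LMM, power increases in proportion to the within person correlation".
- **Aim 3.** After attrition, 180 participants enter Stage 2, which is 90 per pooled arm. The statement is "within-person correlation of 0.60, 2.5% Type-I error, we will have over 80% power to detect a difference of" at least 3.4 points, labelled d = 0.34. It cites a published SMART method but gives no sidedness and no variance formula.
- **Aim 4.** For mediation, "an alpha=0.025, the total sample size is calculated as N=166", again without sidedness.

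The analysis text for Aims 1 to 5 in Sections 9.3.1 to 9.3.3 gives neither an alpha nor a sidedness.

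**The concern.** One error rate is used for three aims and its sidedness is defined for one of them. If the Aim 2 definition carries over, the power stated for Aim 3, and for Aim 2 at follow-up, looks too high for the printed inputs.

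Aim 3 is the trial's Stage 2 question, CC-DBT versus CAMS among insufficient responders. Table 2 lists it with the primary aims; Section 9.3.1 calls it secondary. A CC-DBT advantage with a two-sided p between 0.025 and 0.05 would be positive if 2.5% is one-sided and negative if it is two-sided. That should not be left open until the data are in.

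**Working it through.** **Method.** Non-central t for two equal arms. The non-centrality is d × √(n / 2f), where n is the number per arm and f is the variance factor for the contrast relative to a single measurement:

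- no use of the correlation: f = 1
- baseline-adjusted: f = 1 − r²
- raw change score: f = 2(1 − r)
- end-to-end slope under compound symmetry: f = (1 − r) × T² / Σ(t − t̄)², with T the time span of the contrast

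One-sided 2.5% and two-sided 5% give the same power to the precision used here. Inputs are the d, r and n printed in Section 9.2; visit weeks are from Section 4.2.

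**Step 1: reproduce Aim 2.** d = 0.30, n = 240, f = 1. Non-centrality = 0.30 × √120 = 3.286. Power is 85.0% at two-sided 2.5% and 90.7% at two-sided 5%. The stated 85% therefore fits the level that Aim 2 names.

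**Step 2: Aim 2 at follow-up.** d = 0.30, r = 0.3, n = 240; stated 94%.

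| Contrast | f | Two-sided 2.5% | One-sided 2.5% |
|---|---|---|---|
| Baseline-adjusted | 1 − 0.09 = 0.91 | 88.4% | 93.0% |
| Change score | 2 × 0.7 = 1.4 | 70% | 79% |
| Slope, weeks 0, 3, 6, 10, 14, 26 | 0.7 × 676 / 436.8 = 1.083 | 82% | 88% |

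**Step 3: Aim 3.** d = 0.34, r = 0.60, n = 90; stated over 80%.

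| Contrast | f | Two-sided 2.5% | One-sided 2.5% |
|---|---|---|---|
| Baseline-adjusted | 1 − 0.36 = 0.64 | 72.2% | 80.9% |
| Change score | 2 × 0.4 = 0.8 | 61.4% | 71.8% |
| Slope, weeks 6, 10, 14 | 0.4 × 64 / 32 = 0.8 | 61.4% | 71.8% |
| Slope, weeks 6, 10, 14, 26 | 0.4 × 400 / 224 = 0.714 | 66.9% | not run |

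For the baseline-adjusted row the non-centrality is 0.34 × √(45 / 0.64) = 2.851.

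**Step 4: detectable d for Aim 3 at 80% power** (normal approximation, two-sided 2.5%, where z for 1.25% plus z for 80% power is 3.083).

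- Baseline-adjusted: 3.083 × √(0.64 / 45) = 0.37
- Change score: 3.083 × √(0.8 / 45) = 0.41
- For comparison, baseline-adjusted at one-sided 2.5%: 0.334

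**Step 5: routes that do reach the stated figures at two-sided 2.5%.**

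- Seven equally spaced occasions: f = 0.4 × 36 / 28 = 0.514, giving 82.0% for Aim 3.
- f = 1 − r: 95.3% for Aim 2 follow-up and 91.0% for Aim 3.
- f = 1 / (1 + r): 93.3% for Aim 2 follow-up, but 73.3% for Aim 3.
- 3.4 points over the Aim 2 SD of 7, so d = 0.486: 84.0% for Aim 3 with no correlation credit, 92% as a change score, 96% baseline-adjusted. The printed pair, 3.4 / 0.34, implies an SD of 10.

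**The case against.** A reader might infer that Section 9.2 switched from a two-sided to a one-sided test between paragraphs, and that 94% and over 80% can be obtained only that way. The case against that reading is strong.

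- The documents state no variance formula. Aim 3 rests on a cited method that is not reproduced, so the factor 1 − r² is the checker's choice. Other factors at two-sided 2.5% bracket 94%.
- The Aim 3 model in Section 9.3.2 uses seven occasions, and a slope over seven occasions gives 82% at two-sided 2.5%. An outdated visit schedule could explain over 80% as well as a change of sidedness could.
- A switch of sidedness does not rescue the change contrast, the quantity that the text names: Aim 3 then has 72% and Aim 2 follow-up 79%.
- Aim 3 states no sidedness, and Hypothesis 3 is directional. If one-sided 2.5% was meant, 81% baseline-adjusted agrees with the text.
- With the SD of 7, the 3.4-point difference exceeds 80% power on each contrast tried.
- The sample size is set mainly by Aim 1, and 180 is described as a worst case. With all 240 insufficient responders (120 per arm), baseline-adjusted power at two-sided 2.5% is 85%.

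These arguments defeat the claim that a switch occurred or is the only explanation. They do not restore the stated powers on the current design. The assessments are at baseline and weeks 3, 6, 10, 14 and 26, so the seven-occasion schedule does not exist. The factors 1 − r and 1 / (1 + r) belong to neither a baseline-adjusted nor a change-score comparison. The first would make d of about 0.29 detectable, so 0.34 would be an odd figure to print, and the second leaves Aim 3 at 73%. Using SD 7 contradicts the printed d = 0.34. The directional hypothesis makes a one-sided test possible for Aim 3, but then Section 9.2 uses one label for two error rates and must say so.

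**Conclusion.** The point holds as a gap in specification with two unsupported power figures. Sidedness is defined only for Aim 2. At two-sided 2.5%, with d and r as printed, standard analyses on the current visits give:

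- Aim 3: about 72% (baseline-adjusted) or 61% (change contrast), against over 80%. At d = 0.34, a true effect would be missed about 28% to 39% of the time, rather than less than 20%.
- Aim 2 at follow-up: about 88% (baseline-adjusted) or 70% (change score), against 94%.

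These figures assume equal arms, no clustering by counselor, no loss beyond the planned attrition and, for slopes, compound symmetry. The follow-up correlation of 0.3 is taken as printed although it is labelled for 48 weeks and the visit is at week 26. The Aim 3 result is conditional on d = 0.34 and would change if the SD of 7 applies to the 3.4 points. One-sided testing is a possible cause under baseline adjustment (81% and 93%), not an established one. Aim 2's main 85% is sound, and nothing here bears on the Aim 1 sample size.

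**What to change.** In Sections 9.2 and 9.3, state alpha and sidedness once for Aims 2 to 4. For each power statement, name the contrast, the SD and how the correlation enters. Reconcile 3.4 points, d = 0.34 and SD = 7, then recompute both powers on the visits in Section 4.2.

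- If two-sided 2.5% with baseline adjustment and d as printed is intended, give Aim 2 at follow-up as about 88% and Aim 3 as about 72%, or 80% for d of about 0.37.
- If two-sided 5% is intended, say so and restate Aim 2's 85% as 91%.
- If Aim 3 alone is meant to be one-sided, say so and justify the different error rate.

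The cost is a few sentences and, under the first option, two less favourable power figures. Enrolment does not change. The alpha sentence should be fixed before any comparative results are seen.

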5.4 STRATEGIES FOR RECRUITMENT AND RETENTION

Recruitment and Retention Strategies for Student Participants

Across participating sites, we will recruit a total of 480 student participants for the CAMPUS Trial. Recruitment will take place over 2 years.

Gender. In terms of gender, female students are more likely to seek treatment than male students. This is the case based on data collected at each of the participating sites and in terms of national data for treatment-seeking students.² Therefore, based on site and national data, we are predicting across sites that 60% of participants will be female, 38% will be male, and 2% will be transgender/non-binary. Two important caveats apply here: 1) Although, in general populations, females are more likely to report suicidal ideation than males, that discrepancy appears to not exist among treatment-seeking college students.²¹ Therefore, the estimated gender breakdown will stay the same even among suicidal treatment-seeking college students and this matches our experience in other suicide-focused intervention studies. 2) Currently, approximately 1.6% of treatment-seeking college students nationwide self-identify as transgender or non-binary.²¹ The NIH planned inclusion table does not allow these categories to be entered until the demographic data are in hand. So, it's not going to be reflected in the inclusion table, but it is an important demographic category given the known higher suicide rates for this segment of the population.¹⁸ These data will be collected as part of this study, reflected in recruitment reports later, and gender identity (cisgender vs. transgender/non-binary) will be explored as a moderator of treatment response in this study.

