9.3.3 ANALYSIS OF THE SECONDARY ENDPOINT(S)

AIMS 1-3 analyses are the same as the preceding subsection 9.4.2.

AIM 4 analyses focus on treatment-specific mediation in both CAMS and CC-DBT. The potential mediators (for CC-DBT: DERS, DBT-WCCL, and AAQ; for CAMS: SCS, OHS; Self-Efficacy,) are assessed at baseline, midpoints, and endpoints. To maintain the temporal sequence order of the mediator per Kraemer and colleagues,¹⁶⁵ mediation occurs when, after partialling out the change in the mediator (baseline through midpoints), the relationship between intervention condition and the change in outcome from midpoint(s) through endpoint, when controlling for early change in the outcome (baseline to midpoint), is significantly reduced (in full mediation the relationship is zero). Standard mediation analyses¹⁶⁶ assume sequential ignorability. We will implement causal mediation approaches,^{167,168} as described by MacKinnon and colleagues,¹⁶⁹ which provide an adjustment due to potential unmeasured confounding and the violation of the assumption of sequential ignorability. The analysis team has experience implementing these models.^{170,171} VanderWeele's research team¹⁷² recently described the above mediation technique specifically suited for LMM framed under a generalized mixed effects structure, which we will incorporate. We will fit separate causal mediation models for Stage 1 and Stage 2. Exploratory analyses will focus on multiple mediation and moderated mediation within the causal mediation framework.

AIM 5 analyses focus on moderation within Stage 1 and Stage 2 (gender identity, sexual orientation, minority culture, number of prior suicide attempts, AUDIT, DAST, PAI-BOR, OHS, GAS). A moderator is a baseline characteristic that has a differential effect on outcome across intervention condition¹⁶⁵ and, in the context of a SMART, could be used to further individualize treatment to a particular student participant. Note that a predictor is a non-specific

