moderator—namely, it does not vary by treatment condition. Assessment of moderation will be made by augmenting our outcome analyses described above to include the interaction of the effect of intervention with the potential moderator. Predictor analyses will be conducted in the absence of moderation by removing the interaction term. Additionally, analyses will focus on developing a personalized advantage index (PAI). The PAI was discussed by DeRubeis et al.¹⁷³ as a set of algorithms that can be used to select the optimal treatment for a given patient. Kessler et al.¹⁷⁴ used machine learning methods to develop his selection algorithm. We will do the same with the SAS software procedure PROC QLEARN,¹⁷⁵ which uses the Q-Learning technique described in Nahum-Shani et al.¹⁵⁹

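### Section 9.2 calls the sample sufficient for any moderator, but this does not hold for gender identity, tested on its own, at the predicted 2% share (about 10 of 480 students, about 4 of 180 in Stage 2)

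*Combined protocol and SAP*

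**What the plan says.** Under Power for Aims 4 and 5, section 9.2 relies on Cohen's power tables and describes 480 students at the start of Stage 1, with 90 or more in each Stage 2 arm, as "more than sufficient to detect a medium-to-large ES for a moderator". For moderation it gives no power, alpha, numerical effect size or moderator prevalence.

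Section 5.4 predicts that "60% of participants will be female, 38% will be male, and 2% will be transgender/non-binary", and notes that "approximately 1.6% of treatment-seeking college students nationwide self-identify as transgender or non-binary". It adds that "gender identity (cisgender vs. transgender/non-binary) will be explored as a moderator of treatment response in this study".

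Section 9.3.3 says "AIM 5 analyses focus on moderation within Stage 1 and Stage 2 (gender identity, sexual orientation, minority culture, number of prior suicide attempts", followed by AUDIT, DAST, PAI-BOR, OHS and GAS. Gender identity and sexual orientation are separate entries. The test augments the outcome models to "include the interaction of the effect of intervention with the potential moderator". Where no moderation is found, the interaction term is removed and the variable is analysed as a predictor.

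Table 2 in section 3 differs: Aim 5 and Hypotheses 5a and 5b refer to combined SGM self-identification. Section 9.3.1 classes Aims 2 to 5 as secondary.

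**The concern.** The precision of a treatment-by-subgroup interaction is governed by the smaller subgroup, not by the total sample. Section 9.2 quotes only totals. At the share predicted in section 5.4, the gender-identity interaction would rest on about five transgender or non-binary students per Stage 1 arm and about two per Stage 2 arm.

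What is at stake is how the result would be read. A non-significant interaction would be the likely outcome even if treatment effects differed substantially. Set beside a protocol statement of ample sample size, it could be reported as evidence that treatment works alike in both groups. A significant result would depend on a handful of students. Section 5.4 itself singles out this group as important because of its higher suicide rates, so either misreading would matter.

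**Working it through.** **Inputs from the documents**
- N = 480 in Stage 1, allocated 240:240 (section 4.4).
- N = 180 in Stage 2, 90 per arm (section 9.2): 240 insufficient responders × (1 − 0.25 attrition) = 180.
- Share p = 2%, with 1.6% as the national figure (section 5.4).
- SD of the SSI = 7 and scale range 0 to 38 (sections 9.2 and 8.1).
- Within-person correlation 0.60 (section 9.2, Aim 3), used as a sensitivity value.

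**Assumptions, because the plan is silent**
- Medium-to-large is taken as a difference in treatment effect between subgroups of d = 0.5 to 0.8 SD.
- Two-sided alpha is 0.025, the rate stated for Aims 2 and 3 and for mediation but not for moderation. Alpha 0.05 was also run.

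**The plan's own figures.** There is no moderation power to reproduce. The neighbouring Aim 2 figure does reproduce: 240 per arm, d = 0.30 and alpha 0.025 give 85%. On Cohen's scale, a 1-df interaction F test at alpha 0.025 and N = 180 has power 0.86 at f = 0.25 and 0.999 at f = 0.40; at N = 480 both are at least 0.999. That scale measures variance explained and takes no account of how common the moderator is.

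**Expected counts at 2%.** Stage 1: 480 × 0.02 = 9.6. Stage 2: 180 × 0.02 = 3.6. At 1.6% these become 7.7 and 2.9.

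**Standard error of the interaction, in SD units, with 1:1 arms:** SE = √[4 / (N p (1 − p))].
- Stage 1: √[4 / (480 × 0.02 × 0.98)] = √(4 / 9.408) = 0.652.
- Stage 2: √[4 / (180 × 0.02 × 0.98)] = √(4 / 3.528) = 1.065.

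**Smallest interaction with 80% power:** (z for alpha + 0.842) × SE.
- Alpha 0.025, Stage 1: (2.241 + 0.842) × 0.652 = 2.01 SD, about 14 SSI points.
- Alpha 0.025, Stage 2: (2.241 + 0.842) × 1.065 = 3.28 SD, about 23 of 38 SSI points.
- Alpha 0.05: 1.83 SD and 2.98 SD.

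**Power** (two-sided normal) at d = 0.5 and d = 0.8:

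| Assumption | Stage 1, N = 480 | Stage 2, N = 180 |
|---|---|---|
| 2%, alpha 0.025 | 7% and 16% | 4% and 7% |
| 2%, alpha 0.05 | 12% and 23% | 8% and 12% |
| 2%, alpha 0.025, baseline-adjusted at r = 0.60 | 10% and 24% | 5% and 10% |
| 1.6%, alpha 0.025 | 6% and 13% | 4% and 6% |
| 5% (assumed), alpha 0.025 | 15% and 37% | 7% and 14% |
| 10% (assumed), alpha 0.025 | 27% and 65% | 11% and 26% |
| 50:50 moderator, alpha 0.025 | 69% and 98% | 29% and 67% |

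**Sample size for 80% power** at 2% and alpha 0.025: N = 4 × (2.241 + 0.842)² / (d² × 0.02 × 0.98), about 3,030 for d = 0.8 and 7,760 for d = 0.5.

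**Estimability in Stage 2.** With 90 per arm and no balancing on this category, the chance that at least one arm has no transgender or non-binary student is 1 − (1 − 0.98⁹⁰)² ≈ 30%. The interaction could then not be estimated. Randomization balances on gender (sections 6.1.4 and 6.3), which could lower this figure if the category is used; the documents do not say.

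**Translating Cohen's f.** An interaction with effect f corresponds to d = √[4f² / (p (1 − p))]. At f = 0.25 this is 1.0 SD for a 50:50 moderator. At 2% it is √(0.25 / 0.0196) ≈ 3.6 SD, about 25 SSI points.

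**The case against.** The best defence is that section 9.2 speaks of a moderator in general, cites Cohen's tables and is defensible on their scale. Most of the Aim 5 list consists of counts or scale scores, for which a 2% subgroup does not arise. Section 5.4 says only that gender identity will be explored, and Hypotheses 5a and 5b already use the combined SGM group. The 2% is a forecast, not a quota; the protocol notes higher suicidal ideation among transgender and non-binary people and a growing number of such students, so the trial's share could be larger. Moving from a non-significant interaction to a predictor analysis is routine, and prediction is part of Aim 5 in its own right.

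Much of this stands as a limit on the point. It does not remove it. The sufficiency sentence covers Aim 5 without exception. Aim 5 is a secondary aim, and section 9.3.3 lists gender identity with no exploratory label. Cohen's scale does not help, because f = 0.25 at 2% prevalence means a difference in treatment effect of about 3.6 SD. A share five times the forecast would raise Stage 1 power at 0.8 SD to 65%, but Stage 2 power only to 26%. The predictor step is unobjectionable in itself; the difficulty is treating a test with so little power as having shown that moderation is absent.

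**Conclusion.** For gender identity as a separate moderator, the sufficiency stated in section 9.2 does not hold. At the predicted 2%, power for a 0.5 to 0.8 SD interaction is about 7% to 16% in Stage 1 and 4% to 7% in Stage 2 at alpha 0.025, and 12% to 23% and 8% to 12% at alpha 0.05. The result rests on the 2% forecast and on my readings of effect size and alpha, but no variant tested brings Stage 2 power at 0.8 SD above 26%. The text should be corrected. The primary aim is untouched.

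A reader might infer more than the documents support:
- That section 9.2 is wrong for every moderator. It is defensible on Cohen's scale. The general defect is that effect scale, alpha and prevalence are unstated. Equally, the sentence cannot simply be kept for evenly split moderators: on the SD scale a 50:50 moderator has only 29% to 67% power in Stage 2.
- That sexual orientation or combined SGM status is equally untestable. The documents predict no share for either, so neither adequacy nor inadequacy can be asserted.
- That 0.025 is the plan's alpha for moderation. None is stated.
- That a null result is certain whatever the truth. In Stage 1 at 0.8 SD, power is 16% to 24% across the alpha and baseline-adjustment variants at 2%: low, but not nil.

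**What to change.** **Section 9.2.** Replace the blanket sentence with the interaction effect detectable at 80% power in each stage, stating the alpha, the effect scale and the moderator prevalence assumed. A 50:50 binary moderator at alpha 0.025 would give 0.56 SD in Stage 1 and 0.92 SD in Stage 2. State that sufficiency does not hold for gender identity at the predicted 2%.

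**Section 9.3.3, Aim 5.** Use the combined SGM indicator of Hypotheses 5a and 5b as the tested moderator that covers gender identity, without asserting its power. Report gender identity alone descriptively, with treatment-effect estimates and confidence intervals where they can be estimated. Say that a non-significant interaction will not be read as absence of moderation. Leave the separate sexual-orientation test in place.

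**Cost.** Wording only, with no new data or visits. The loss is a formal gender-identity interaction test whose power for 0.5 to 0.8 SD at the predicted share is 4% to 16% at alpha 0.025, and at most 23% at alpha 0.05 without baseline adjustment.
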